4.6 Insurance

In case of any damage or injury occurring during the participation in the investigation, the Sponsor has contracted an insurance company (Willis), which will cover the liability of the Sponsor, the investigators and other persons involved in the investigation. The Sponsor may use a local insurance company, where applicable, according to national legislation.

5 Design of the clinical investigation

The investigation is designed as an international multicentre, open, prospective clinical investigation. The investigation comprises a 6-month investigation with an additional 18-month follow-up period.

5.1 Rationale for the design of the clinical investigation

This investigation is designed to collect data regarding the usability and clinical performance of the Baha Attract System in subjects with hearing impairment that are candidates for Baha surgery.

The investigation will be performed in an open design since it is not possible to perform the investigation in a blinded fashion. The main evaluations of the investigation, i.e. free-field hearing tests, are relevant and objective methods.

This investigation is expected to demonstrate that the Baha Attract System performs within its intended use and is a suitable treatment for patients with a conductive or mixed hearing loss or single-sided sensorineural deafness.

While the Baha Attract System is approved for use in both adults and children, this investigation is limited to adult subjects. The paediatric population constitutes an inhomogeneous patient group (age-related), and currently there are no audiological tests that are suitable for comparisons across age ranges and across multiple countries/languages. Performance evaluation of the Baha Attract System in children should be performed as separate investigations.

5.2 Variables

5.2.1 Primary efficacy variable

Free-field hearing tests: Thresholds audiometry – Pure Tone Average PTA4 (Mean of 500Hz, 1000Hz, 2000Hz and 4000Hz).

5.2.2 Secondary efficacy variables

The secondary efficacy variables will be evaluated as follows:

- Free-field hearing tests:
 - Threshold audiometry (pure tones): 250, 500, 1000, 2000, 3000, 4000 and 6000Hz
 - Adaptive speech recognition in noise (50% performance)
 - Speech in quiet (50dB, 65dB and 80dB SPL)
- BC Direct thresholds
- Questionnaires:

- Generic quality of life scale: Health Utility Index (HUI):
 - o *Health related quality of life score for overall health*
 - o *Vision score*
 - o *Hearing score*
 - o *Speech score*
 - o *Ambulation/mobility score*
 - o *Dexterity score*
 - o *Self-care score*
 - o *Emotion score*
 - o *Cognition score*

- Abbreviated Profile of Hearing Aid Benefit (APHAB):
 - o *Ease of Communication*
 - o *Reverberation*
 - o *Background Noise*
 - o *Aversiveness*
 - o *Global score*

- The Speech, Spatial and Qualities of Hearing Scale (SSQ)

- Surgical information:
 - Skin thickness
 - Surgery time
 - Soft tissue flap thinning
 - Bone polishing/removal
 - Implant stability quotient (ISQ)

- Sound processor selection

- Choice of SP Magnet

- Magnetic retention force (dynamometer)

- Questions regarding:
 - Daily use of sound processor (hours)
 - Magnetic retention
 - Change of Soft pad

5.2.3 Safety variables

- Pain/discomfort
- Numbness
- Soft tissue status

- Loss/removal of Implant and/or Implant Magnet
- Device deficiency
- Concomitant medication
- Adverse Events and Adverse Device Effect
- Serious Adverse Events and Serious Adverse Device Effects

5.2.4 Demographics and baseline variables

- Demographics
- Medical and surgical history
 - Type of hearing loss
 - Aetiology of hearing loss
 - Current conventional hearing aid
 - Current/previous medications and treatments
- Nicotine use
- Audiogram
- Skin thickness

5.3 Investigational flowchart

Procedures and timing	Visit 1 Softband test	Visit 2 Surgery	Visit 3 Suture removal	Visit 4 Fitting	Visit 5	Visit 6	Visit 7	Visit 8	Visit 9
Day/Week/Month ¹	Pre-op	D 0	D 10	W 4	W 6	W 12	M 6	M 12	M 24
Time window			± 5d	± 1w	± 1w	± 2w	± 4w	± 4w	± 4w
Demographics	X								
Medical history	X								
Nicotine use	X								
Audiogram ²	X								
Eligibility criteria	X								
Informed consent	X								
Soft tissue thickness	X	or X							
Health Utility Index (HUI) ³	X ⁴						X		X
Abbreviated Profile of Hearing Aid Benefit (APHAB) ³	X ^{4,5}						X ⁶		X ⁶
The Speech, Spatial and Qualities of Hearing Scale (SSQ) ³	X ^{4,5}						X ⁶		X ⁶
BC Direct using BFS	X ⁷			X ⁸					
Selection of sound processor	X								
Change of sound processor				X ⁹	X ⁹	X ⁹	X ⁹	X ⁹	X ⁹
Fitting of sound processor	X ⁷			X ⁸					
Fine tuning of sound processor					X ⁹	X ⁹	X ⁹	X ⁹	X ⁹
Free field thresholds	X ^{5,7}			X ⁸			X ⁸	X ⁸	X ⁸
Speech recognition in noise	X ^{5,7}			X ⁸			X ⁸	X ⁸	X ⁸
Speech recognition in quiet	X ^{5,7}			X ⁸			X ⁸	X ⁸	X ⁸
Home test of sound processor on Softband	X →								
Surgery		X							
Surgery time		X							
Soft tissue thinning		X							
Bone polishing/removal		X							
Implant stability quotient		X							
Suture removal (if applicable)			X						
SP Magnet selection				X					
Magnetic retention force				X	X	X	X	X	X
Change of SP Magnet					X ⁹	X ⁹	X ⁹	X ⁹	X ⁹
Questions regarding: • Daily use of sound processor • Magnet retention • Change of Soft pad					X	X	X	X	X
Pain/discomfort					X	X	X	X	X
Numbness			X	X	X	X	X	X	X
Soft tissue status			X	X	X	X	X	X	X
Loss/removal of Implant or Implant Magnet			X	X	X	X	X	X	X
Device deficiency		X	X	X	X	X	X	X	X
Adverse Events		X	X	X	X	X	X	X	X
Concomitant medication/treatment	X	X	X	X	X	X	X	X	X
Extra visit									

¹ The time between visits will be calculated from Visit 2 (time 0); ² Only if the last audiogram that was performed on the subject is older than 6 months; ³ To be completed by the subject; ⁴ Before Softband test; ⁵ Unaided; ⁶ Aided; ⁷ With sound processor on Softband; ⁸ With Baha Attract System; ⁹ If needed.

6 Procedures

6.1 Subject demographics

The following demographic data will be recorded at the baseline visit, Visit 1:

- Date of birth (month and year)
- Gender
- Ethnic background
- Weight and height

6.2 Medical history

The following subject characteristics will be recorded at the baseline visit, Visit 1:

- Type of hearing loss
- Aetiology of hearing loss
- Current conventional hearing aid
- Relevant medical and surgical history during the past five years as judged by the investigator
- Current concomitant medication and treatments

6.3 Nicotine use

Use of nicotine should be assessed using the following scale:

0	Does not smoke	
1	Less than 10 cigarettes/day	Low consumption
2	Between 11 and 20 cigarettes/day	Medium consumption
3	Between 21 and 40 cigarettes/day	High consumption
4	More than 40 cigarettes/day	Very high consumption

6.4 Audiogram

Unaided audiometric threshold measures (including both air- and bone conduction thresholds) should demonstrate that the subject has a conductive or mixed hearing loss or single-sided sensorineural deafness. An existing audiogram may be used as long as it has been completed during the last six months. The subject's pre-operative Pure Tone Average PTA4 (mean of 500, 1000, 2000 and 4000Hz) should be recorded to ensure the subject meets the inclusion criteria.

6.5 Soft tissue thickness

At Visit 1 or Visit 2, the surgeon should measure the soft tissue thickness at the planned implant site. A hypodermic needle, a clamp and a ruler should be used. Topical anaesthetic may be used at the discretion of the investigator. Local anaesthetic given as a subcutaneous injection should **not be used prior to** soft tissue thickness measurement since the thickness will be affected. In order to obtain a correct measurement, care must be taken to not depress the skin with the needle, fingers and/or clamp.

Subjects with a soft tissue thickness of less than 3 mm should be excluded from the investigation. Subjects with a soft tissue thickness exceeding 6 mm at the planned location of the Implant Magnet will require surgical thinning of the soft tissue flap.

[figure not shown]

Figure 6. Measuring soft tissue thickness

6.6 Health Utility Index (HUI)

The Health Utilities Index (HUI®) is a generic preference-based system for measuring comprehensive health status and health-related quality of life (HRQL). HUI provides descriptive evidence on multiple dimensions of health status, a score for each dimension of health, and a HRQL score for overall health. Health dimensions include vision, hearing, speech, ambulation/mobility, pain, dexterity, self-care, emotion and cognition. Each dimension has 3-6 levels.

The subjects will complete the HUI Mark 3 (HUI3) at Visit 1, 7 and 9.

At Visit 1, the subjects will complete the HUI3 questionnaire prior to the Softband test.

6.7 The Abbreviated Profile of Hearing Aid Benefit (APHAB)

The APHAB is a 24-item self-assessment inventory that evaluates the benefit experienced by the subject when using hearing amplification compared to the unaided situation. The APHAB produces a global score and scores for four subscales: ease of communication (EC), reverberation (RV), background noise (BN), and aversiveness (AV).

The subjects will complete the APHAB questionnaire at Visit 1, 7 and 9.

At Visit 1, the subjects shall complete the questionnaire prior to the Softband test. At Visit 1, the questionnaire shall be answered with respect to the subject's **unaided** hearing.

At Visit 7 and 9, the subjects shall complete the questionnaire for the **aided** situation (with the Baha Attract System).

6.8 Speech, Spatial, and Qualities of Hearing Scale (SSQ)

The Speech, Spatial, and Qualities of Hearing (SSQ) questionnaire is designed to measure self-reported auditory disability across a wide variety of domains, reflecting the reality of hearing in the everyday world. It covers:

- Hearing speech in a variety of competing contexts
- The directional, distance and movement components of spatial hearing
- Segregation of sounds and attending to simultaneous speech streams
- Ease of listening
- The naturalness, clarity and identifiability of different speakers, different musical pieces and instruments, and different everyday sounds

The subjects will complete the SSQ at Visit 1, 7 and 9.

At Visit 1, the subjects shall complete the SSQ questionnaire prior to the Softband test. At Visit 1, the SSQ shall be answered with respect to the subject's **unaided** hearing, even for subjects with a previous hearing device.

At Visit 7 and 9, the subjects shall complete the questionnaire for the **aided** situation (with the Baha Attract System).

6.9 Sound processor selection

Based on results from BC Direct tests (see section 6.10 for details) performed with the sound processor on a Baha Softband at Visit 1, the audiologist will select an appropriate Baha sound processor for the subject. The Baha BP110 Sound Processor, the Baha 4 Sound Processor or future generation regulatory approved sound processors shall be used. If deemed necessary, the audiologist shall adjust the sound processor gain until satisfied, as judged by the investigator and subject.

During the selection process all the three free-field tests must be performed on the selected sound processor and the chosen setting, i.e:

- Threshold audiometry – free field
- Adaptive speech recognition in noise
- Speech recognition in quiet

The selected sound processor should be used during the Softband testing period and then attached to the SP Magnet at Visit 4. The subject will receive a user manual for the selected sound processor.

If the subject is unsatisfied or experiences extensive feedback noise, the audiologist may switch to a more powerful sound processor.

6.10 Bone Conduction (BC) Direct

BC Direct is a tool in the Cochlear Baha Fitting Software to establish the unmasked bone condition threshold with tones presented through the sound processor. At Visit 1, BC Direct data shall be collected with the selected sound processor on a Baha Softband and shall be used to calculate the fitting (settings) of the sound processor for the Softband test period (see section 6.15). BC Direct and the fitting procedure will also be performed at Visit 4 when the subject will start to use the sound processor connected to the SP Magnet.

Baha Fitting Software 4.0 or future generation Baha Fitting Software will be used. Feedback management (part of Fitting Software) should be used when fitting the device.

Figure 7. Performing BC Direct on Softband.

6.11 Fine tuning of Baha sound processor

If the subject experiences problem with the performance of the sound processor (e.g. feedback, loudness, poor sound quality) the audiologist should change the sound processor settings utilising Baha Fitting Software 4.0 or future generation Baha Fitting Software. BC Direct should be performed and the sound processor should be re-prescribed. **The same procedure shall also be performed each time a subject requires a change of the SP Magnet.**

6.12 Free field pure tone thresholds

The purpose of this test is to establish the hearing thresholds for pure tones presented in free field through a speaker in front position (0 degrees azimuth) according to the so-called ascending or modified Hughson-Westlake method. During the test, the signal processing of the sound processor shall be set to omnidirectional mode. The test shall be performed with the non-test ear blocked (in case of normal or near-normal hearing or a large asymmetry with the non-test ear having significantly better hearing thresholds).

At Visit 1, free-field thresholds shall be measured for the unaided situation and with the selected sound processor on a Baha Softband. At Visit 4, 7, 8 and 9, the same test shall be performed with the selected sound processor and selected SP Magnet.

Figure 8. Free field front speaker position.

6.13 Speech recognition of words in quiet

The purpose of this test is to establish the test subject's maximum speech recognition in quiet. The speech test in quiet shall be performed using phonetically balanced words presented from the front (0 degrees azimuth). The test material shall be single syllable words and presented at 50, 65 and 80 dB sound pressure level (SPL) and scores shall be recorded as % correct words at each presentation level. During the test, the signal processing of the sound processor shall be set to omnidirectional mode. The test shall be performed with the non-test ear blocked (in case of normal or near-normal hearing or a large asymmetry with the non-test ear having significantly better hearing thresholds).

At Visit 1, the speech in quiet test shall be performed for the unaided situation and with the selected sound processor on a Baha Softband. At Visit 4, 7, 8 and 9, the same test shall be performed with the selected sound processor and selected SP Magnet.

6.14 Adaptive sentence recognition in noise

The purpose of this test is to establish the test subject's ability to recognise speech in the presence of background noise. The adaptive speech test in noise shall be conducted using validated lists of phonetically balanced sentences, with speech presented from the front (0 degrees azimuth) and noise from the back (180 degrees azimuth). The noise shall be kept constant at 65 dB SPL, and the speech shall be adapted in 2 dB steps to establish the speech-to-noise ratio (SNR) providing a 50% level of understanding. During the test, the signal processing of the sound processor shall be set to omnidirectional mode. The test shall be performed with the non-test ear blocked (in case of normal or near-normal hearing or a large asymmetry with the non-test ear having significantly better hearing thresholds).

At Visit 1, the speech in noise test shall be performed for the unaided situation and with the selected sound processor on a Baha Softband. At Visit 4, 7, 8 and 9, the same test shall be performed with the selected sound processor and selected SP Magnet.

6.15 Test of Sound Processor on Softband

Between Visit 1 and Visit 2 (pre-operatively), the subjects will use the Baha Softband to test the sound processor during 1-2 weeks in different daily listening situations in order to get an impression of the hearing improvement he/she might anticipate post-surgery with the sound processor connected to the SP Magnet. The subject will use the selected sound processor as described in section 6.9. Instructions regarding use of the Baha Softband are described in the user manual for the product.

6.16 Surgery

Surgery will be performed at Visit 2 in accordance with the procedure described in the Surgery Guide for the Baha Attract System. Surgery may be performed under general anaesthesia or by using local anaesthetic at the discretion of the investigator. The following information will be collected:

- **Surgery time**
The surgery time is measured from the time from first incision to suture closure.
- **Soft tissue thinning performed**
Surgical thinning of the soft tissue flap must be performed if the thickness exceeds 6 mm. If soft tissue thinning is performed, the extent of flap thinning (in mm) shall be recorded.
- **Bone polishing/removal performed**
Any use of bone polishing to accommodate the Implant Magnet shall be recorded.
- **Implant stability quotient (ISQ)**
Implant stability shall be measured during surgery using resonance frequency analysis. The measurement renders an implant stability quotient (ISQ) value between 1 and 100. The measurement shall be performed at the implant level after inserting the BI300 Implant and before attaching the Implant Magnet to the Implant. The highest and lowest ISQ value out of two perpendicular measurements shall be recorded, ISQ High and ISQ Low. The Osstell ISQ instrument and SmartPeg Type 30 (Osstell, Gothenburg, Sweden) shall be used. The procedure for obtaining ISQ values is described in Appendix 1.

After surgery, the subject will receive instructions as for how to take care of the skin in accordance with local practice. The subject will also receive a Magnetic Resonance Imaging (MRI) card, which contains information to professional health care providers regarding the implanted magnet.

6.17 Removal of sutures

The sutures shall be removed at Visit 3 (i.e. 10 days after surgery), if applicable. The surgeon/surgical nurse will determine if the wound requires further wound dressings, and if so, extra visit(s) will be scheduled, until the wound is considered healed.

6.18 Baha sound processor fitting on SP Magnet

The Baha sound processor that was selected during the initial sound processor selection at Visit 1 (see Section 6.9) will be fitted with the SP Magnet to the implant at Visit 4 (i.e. 4 weeks after surgery). A suitable SP Magnet shall be selected as described in Section 6.19. Sound processor fitting shall be performed in accordance with the information in the Fitting Guide (Baha Fitting Software 4.0 or later generation). If the wound is not considered sufficiently healed, as judged by the surgeon/surgical nurse, the installation shall be delayed to a scheduled subsequent visit or extra visit, when the site is considered sufficiently healed.

The subject will receive a User Guide, which contains important information regarding the device.

6.19 SP Magnet selection

Initial SP Magnet selection shall be performed at the time of fitting the Baha sound processor to the SP Magnet at Visit 4 (see Section 6.18). During follow-up, a change to a stronger or weaker SP Magnet may be required. A decision regarding SP Magnet strength shall be made at Visit 4-9 and at any extra visit. SP Magnet selection shall be performed in accordance with the procedure described in the SP Magnet Selection Guide for the Baha Attract System. When selecting an SP Magnet it is important to choose the SP Magnet that provides the best possible retention while still being comfortable for the subject.

If a subject requires an SP Magnet change, BC Direct shall be performed with the new SP Magnet and the device shall be re-prescribed.

6.20 Magnetic retention force

The magnetic retention force of the SP Magnet shall be measured at Visit 4-9 and at any extra visits including a change of SP Magnet. A specific Force Measuring Tool (dynamometer) shall be used. The measurement will be repeated three times. For each measurement the SP Magnet should be placed on the skin above the Implant Magnet and the measurement should be performed after one minute in order for the Soft pad to be compressed.

6.21 Daily use, retention, change of Soft pads

At Visits 5-9 subjects will be asked about the following topics:

- **Daily use of sound processor**
Average hours of daily use (hours/day) during the last week before Visit 5, and during the last month before Visit 6-9.
- **Insufficient retention (number of episodes)**
Number of times the device fell off during the last week before Visit 5-9?
- **Change of Soft pads (frequency)**
Number of times the subject changed the Soft pad during the last week before Visit 5, and during the last month before Visit 6-9?

6.22 Pain/discomfort

The subject will be asked about the level of discomfort and/or pain at Visits 5-9 using the following scale:

- Which of the following alternatives corresponds best to the subject's experience with the Baha Attract System?
 - 0 = No discomfort and/or pain. Normal daily use of sound processor.
 - 1 = Slight discomfort and/or pain, not significantly affecting daily use of sound processor.
 - 2 = Discomfort and/or pain, reducing daily use of sound processor.
 - 3 = Excessive discomfort and/or pain, preventing use of sound processor.

6.23 Soft tissue status

At Visit 3-9, the investigator will examine the soft tissue at the implant site. In case of signs of e.g. inflammation, infection, skin necrosis or scar hypertrophy, the event shall be reported on the Adverse Event page in the CRF. If any treatment is provided, it shall also be recorded on the Concomitant medication page in the CRF.

6.24 Numbness

Subjects will be assessed for any presence of numbness around in the implant area at Visits 3-9. The following scale will be used:

1. No numbness
2. Numbness within 2 cm from the implant (center of the inner magnet)
3. Numbness within and beyond 2 cm from the implant (center of the inner magnet)

Numbness will be assessed by means of a pin and a cotton swab. Randomly picked locations in and around the implant area (within and beyond 2 cm from the centre of the implant magnet) will be tested by gently touching the skin with the pin and the cotton swab. The scale above shall be used to score the subject's sensation to stimulus with the pin and with the cotton swab.

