3.1 Device tested in the investigation

The device tested in the investigation is the Cochlear™ Baha® Attract System. The device is CE marked in the EU and registered as a 510(k) device in the US for the intended use described in this CIP.

The Cochlear Baha Attract System incorporates implantable and external parts as illustrated in Figure 1. The implantable parts include the BI300 Implant and the BIM400 Implant Magnet, which is intended to be fixated to the BI300 Implant. The external parts include the Sound Processor Magnet (SP Magnet), which, together with the Implant Magnet, constitute the transcutaneous coupling. The SP Magnet incorporates a soft material (Soft pad) at the tissue facing surface that is designed to distribute the pressure over the skin. The Baha Sound Processor attaches to the SP Magnet via a snap coupling.

[figure not shown]

Figure 1. From left to right: BI300 Implant, BIM400 Implant Magnet, SP Magnet with Soft pad, and sound processor.

The different parts of the Cochlear™ Baha® Attract System are described in more detail below:

- **BI300 Implant** (Article # 92128, 92129)

The BI300 Implant is a screw-shaped titanium implant with a titanium dioxide-blasted surface (TiOBlast™). The implant has a diameter of 4.5 mm and is available in two different lengths, 4 mm and 3 mm. The implant is intended to be fixated and become osseointegrated in the skull bone. The BI300 Implant is delivered sterile for single-use.

- **BIM400 Implant Magnet** (Article # 93550)

The BIM400 Implant Magnet comprises an implantable hermetically sealed titanium casing (round shape, diameter: 27 mm, surface area: 5.7 cm²) including two magnets (north and south pole) in half ring shape. The Implant Magnet is fixated to the BI300 Implant with a fixation screw and lies completely under the skin. The Implant Magnet is delivered sterile for single-use.

Figure 2. Implant Magnet

- **SP Magnet** (Article # 93561, 93562, 93563, 93564, 93565, 93566¹)

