3.3.2 Pain and numbness

- Pain/discomfort (w 6, w 12, m 6, m 12 and m 24)
 - No discomfort and/or pain.
 - Slight discomfort and/or pain
 - Discomfort and/or pain
 - Excessive discomfort and/or pain
- Numbness (pin) (d 10, w 4, w 6, w 12, m 6, m 12 and m 24)
 - No numbness
 - Numbness within 2 cm from the implant
 - Numbness within and beyond 2 cm from the implant
- Numbness (cotton swab) (d 10, w 4, w 6, w 12, m 6, m 12 and m 24)
 - No numbness
 - Numbness within 2 cm from the implant
 - Numbness within and beyond 2 cm from the implant

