4.11.2 Pain/discomfort, Numbness, Device deficiency and Soft tissue status

Pain/discomfort, Numbness, Device deficiency and Soft tissue status will be presented by visit.

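### The three-level numbness scale has no place for numbness found only beyond 2 cm, although the procedure tests that zone

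*Protocol*

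**What the plan says.** Protocol 6.24 sets the timing: "Subjects will be assessed for any presence of numbness around in the implant area at Visits 3-9". Testing covers two zones: "Randomly picked locations in and around the implant area (within and beyond 2 cm from the centre of the implant magnet) will be tested".

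The scale has three levels. The first is no numbness. The second is "Numbness within 2 cm from the implant (center of the inner magnet"). The third is "Numbness within and beyond 2 cm from the implant (center of the inner magnet"). One scale serves both stimuli: "The scale above shall be used to score the subject's sensation to stimulus with the pin and with the cotton swab".

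SAP 3.3.2 carries the same three levels into the analysis, separately for pin and for cotton swab, at day 10, weeks 4, 6 and 12, and months 6, 12 and 24. Its top level reads "Numbness within and beyond 2 cm from the implant". It has no beyond-only level, no other category and no rule for findings that do not fit.

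On analysis, SAP 4.11.2 says: "Pain/discomfort, Numbness, Device deficiency and Soft tissue status will be presented by visit". The output is Table 14.3.2 in the Safety population. Protocol 8.6.1 makes all safety variables descriptive.

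**The concern.** The procedure and the scale do not match. The procedure examines the inner and outer zones and can therefore find numbness in either one alone. The scale recognises outer numbness only when inner numbness is present too.

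A subject who is numb only outside the circle leaves the assessor four choices:

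- no numbness, which hides a finding that the section sets out to detect;
- within 2 cm, which puts it in the wrong place;
- within and beyond 2 cm, which overstates its extent;
- a blank.

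The documents do not say which to use, so assessors at the five sites listed in SAP 3.1.1 may choose differently. A blank also has no stated handling, because the imputation rules in SAP 4.1 apply to efficacy variables only.

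Collecting information on numbness is part of a secondary objective (protocol 1.3.2), and numbness is a listed safety variable (protocol 5.2.3). What is at stake is whether the by-visit table gives its prevalence and extent correctly.

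**Working it through.** The plan states no rate, power or sample size for numbness, so there is no figure of its own to reproduce. The check is an enumeration, with some arithmetic on geometry and scale.

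**1. Patterns against levels** (protocol 6.24; SAP 3.3.2)

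| Numb within 2 cm | Numb beyond 2 cm | Level available |
|---|---|---|
| No | No | 1 |
| Yes | No | 2 |
| Yes | Yes | 3 |
| No | Yes | none |

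Three of the four patterns have a level. If level 2 is read loosely, as any inner numbness, the last row is still empty.

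**2. Where the boundary lies.** Protocol 3.1 gives the Implant Magnet as "round shape, diameter: 27 mm, surface area: 5.7 cm²". Its radius is 27/2 = 13.5 mm. The circle is centred on the magnet, so it ends 20 − 13.5 = 6.5 mm outside the magnet's edge. The outer zone therefore starts close to the device. This shows that outer-only numbness is possible, not how often it occurs.

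**3. Exposure.** Seven visits × 2 stimuli = up to 14 scores per subject, all on this scale.

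**4. Effect on the table.** If all 52 planned subjects are operated on and assessed (an assumption), one misplaced subject moves a category by 1/52 = 1.9 percentage points at that visit. The number of such subjects cannot be derived from the documents.

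**5. Can sampling produce the missing pattern?** Suppose a subject is truly numb in both zones, a fraction f of each zone is numb, and k independent random points are tested per zone. The documents give neither f nor k, so both are assumed. A zone is missed with probability m = (1 − f)^k. The chance of observing outer numbness only is m(1 − m).

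| f | k | m | m(1 − m) |
|---|---|---|---|
| 0.10 | 2 | 0.81 | 0.15 |
| 0.25 | 2 | 0.56 | 0.25 |
| 0.25 | 4 | 0.32 | 0.22 |
| 0.50 | 4 | 0.06 | 0.06 |
| 0.50 | 8 | 0.004 | 0.004 |

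So the unscorable pattern could also arise in a true level 3 subject. Depending on the assumptions, the chance runs from negligible to about one in four.

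**The case against.** **The effect may be small.** The documents give no incision position, flap extent or frequency of outer-only numbness, and protocol 6.16 leaves the procedure to a separate Surgery Guide. This stands: the geometry supports possibility only.

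**Clinically relevant outer numbness has another route.** The adverse event definition in protocol 6.27.1 covers untoward clinical signs and procedure-related events, and SAP 3.3.1 codes events outside the predefined categories. This limits the consequence but does not repair the numbness table. The CRF is not among the documents and might allow a comment, but SAP 3.3.2 has no category to receive one.

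**A sensible assessor would use level 3 for any numbness reaching beyond 2 cm.** Some may. The wording does not say so, and the result would still overstate extent.

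**A stronger reading is tempting.** A reader might infer that points are redrawn at each visit, so that scores drift by sampling and the apparent recovery over time is distorted. The documents do not support that. Protocol 6.24 says the locations are picked at random, but not how many there are or whether they are reused. Numbness is only described by visit, and no table of within-subject change is listed. With constant true numbness and constant testing effort, random points give the same expected percentages at every visit, so no group trend is created. Nor is a fixed map of points a demonstrated correction. Under the model above, four fixed points miss a patch covering 20% of a zone as often as four random ones (0.8^4 = 0.41), and then keep missing it if it does not change.

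**Conclusion.** The scale is not exhaustive. Following protocol 6.24 exactly can produce a finding that the three levels cannot record truthfully, and SAP 3.3.2 inherits the gap. This follows from the wording alone and needs no assumption. It is a defect in a stated rule rather than a missing detail.

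The size of the effect is unknown, because the frequency of outer-only numbness is not given. The 1.9 points per subject assumes that all 52 are operated on and assessed, and the sampling probabilities in the working are illustrations on assumed inputs. The damage is confined to the numbness part of Table 14.3.2. No hypothesis test, significance level or sample size is touched. The point deserves correction because the change is cheap, not because a conclusion of the trial depends on it.

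**What to change.** In protocol 6.24, the CRF and SAP 3.3.2, replace the single score by two yes/no items, numbness within 2 cm and numbness beyond 2 cm, recorded separately for pin and for cotton swab. Tabulate all four patterns by visit in Table 14.3.2. The minimum change is to add a beyond-2-cm-only category to the present scale. Widening level 3 to any numbness beyond 2 cm would also close the gap, but it merges two patterns that separate items keep apart.

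Optionally, state a minimum number of test points per zone, the same at every visit. This makes testing effort comparable across visits and sites, but the main correction does not depend on it.

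Cost: wording in three documents, and four yes/no entries per visit in place of two scores. No extra visit or instrument is needed. The drawback is that scores collected before the change keep the old definition. They must be flagged in the table, and beyond-only cases already recorded as level 1, 2 or 3 cannot be recovered.
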